#### Self-Assessment Questionnaire

This study used well-validated instruments with good reliability, including the Beck Depression Inventory-II (BDI-II), the Beck Anxiety Inventory (BAI), the Chinese version of the Occupational Self-Assessment (OSA), the Chinese version of the Canadian Occupational Performance Measure (COPM), and the Taiwan version of the World Health Organization Quality of Life-BREF (WHOQOL-BREF-TW) in both pre- and post-tests (with BDI-II used for case screening only). These tools assessed the level of depression, anxiety, self-efficacy, environmental support, occupational performance issues and changes, and quality of life.

#### Qualitative Feedback Information

One week after the intervention ends, the researcher would design a questionnaire for participants to evaluate the effectiveness and practicality of the online "Mindfulness Cognitive Skills" program. This would include qualitative interview questions and quantitative items for participants to rate. The purpose was to understand whether the eight-week online study meets the needs of the participants, assisted in learning and managing self-emotions, and to gather feedback on usage after the study and suggestions for the research.

### 2.4 Analyses

The study would use descriptive statistics to record and analyze the basic information and follow-up measurement data of the participants, described in terms of percentages, means, and standard deviations. Changes in depression levels and quality of life between the experimental and control groups would be analyzed using a mixed-effects model to verify the effectiveness of the "Online Mindfulness Cognitive Skills" program on depression and quality of life among students with depressive tendencies. The analysis would be conducted using SAS 9.4 statistical software, with a significance level set at  $\alpha = 0.05$ .

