### 2.1 Study design

Participants in the experimental group would be arranged to attend online mindfulness-based cognitive programs for eight weeks. Each week was divided into 3 parts: detailed skill training with pictures or short videos, techniques application in different scenarios, and concepts consolidation through a web-based assignment.

Participants were requested to complete the 3 parts above, which would take approximately 15 minutes in total per week. The content of the online intervention includes 8 chapters reflecting multiple topics (e.g. explaining MBCT, automatic pilot, awareness of mood, accentedness, staying with the present experience, linking habitual reactions to the unpleasant event, using breathing and body as an anchor, and planning to continue mindfulness practice) which were delivered to subjects each week by the research team.

Participants in the control group would acquire knowledge of mental health to manage their negative emotions. There would be 2 times of mental health education and one web-based assignment including writing feedback to ensure learning effectiveness each week. The content for 8 weeks would include knowledge about depression, recognition of depression and depressive mood, symptom management, adaptation skills and coping skills, myths of depression, depression prevention, and referral information for mental health. The investigators would evaluate the effectiveness of the two groups using the outcome assessment of BDI-II, WHOQOL-BREF, BAI, OSA, and COPM 1 week before intervention (pre-test) and 1 week after intervention (post-test).

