### 2.2 Populations and subgroups to be analysed

This study would use a Survey Cake form, announced through the university website or online platforms, to recruit participants, primarily targeting undergraduate students at a certain medical university in Taichung, Taiwan. Participants would be screened through the BDI-II and the basic information questionnaire. The inclusion criteria were as follows: (1) aged between 18 and 25 years; (2) scoring at least mild on the Beck Depression Inventory-II (BDI-II); (3) having the LINE messaging application; and (4) being literate and willing to participate in the study. Exclusion criteria were: (1) self-reported other mental illnesses such as schizophrenia or bipolar disorder; (2)

self-reported major physical illnesses such as cancer or stroke; and (3) unwillingness to accept random assignment. The sample size was estimated that a correlational study requires at least 30 participants. Considering potential dropouts or inability to complete the online study, a 35% attrition rate was applied, resulting in a minimum of 46 valid questionnaires being collected. Participants would then be randomly assigned, with 23 in the experimental group and 23 in the control group.

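### Section 2.4 compares changes between arms and makes no use of the pre-test for adjustment; at an assumed pre/post correlation of 0.7 to 0.3 this leaves about 7–23% avoidable variance for quality of life, and less for BDI-II.

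*Combined protocol and SAP*

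**What the plan says.** Section 2.4 gives the comparative analysis in one sentence: "Changes in depression levels and quality of life between the experimental and control groups would be analyzed using a mixed-effects model". The next sentence names the software and alpha. The section does not state the fixed effects, the contrast to be tested, the covariance structure or how the pre-test enters. No other section mentions baseline adjustment.

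Section 2.1 sets one measurement before and one after the programme, "using the outcome assessment of BDI-II, WHOQOL-BREF, BAI, OSA, and COPM 1 week before intervention (pre-test) and 1 week after intervention (post-test"). Section 2.3 (Self-Assessment Questionnaire) also lists the instruments at both times, but adds "with BDI-II used for case screening only". Section 2.2 requires "scoring at least mild on the Beck Depression Inventory-II (BDI-II") for entry. On numbers, it says "a 35% attrition rate was applied, resulting in a minimum of 46 valid questionnaires being collected", with 23 allocated to each arm.

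**The concern.** With two time points, a mixed model has repeated measures only if the pre-test is itself an outcome row. A sentence about changes between groups then most naturally describes the group-by-time term with a separate baseline mean per arm. With complete data this equals the difference in mean change scores.

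That analysis is valid. Under randomisation, however, the two arms share a baseline mean, so any observed pre-test difference is chance. The unconstrained contrast subtracts that difference in full, although regression to the mean implies that only a fraction of it carries over to the post-test. The excess is noise that the trial's own data could remove.

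Two things are at stake. With about 30 completers in total, precision is scarce. The sentence also permits several analyses (group-by-time, common baseline, pre-test as covariate, raw change scores) with different standard errors, and the choice among them is left open.

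**Working it through.** **Inputs from the document.** There are 23 randomised per arm, 35% attrition, and one pre-test and one post-test; alpha is 0.05 (Sections 2.1, 2.2 and 2.4). The stated total follows from the base of 30: 30/0.65 = 46.15, given as 46 (47 if rounded up). Expected post-tests per arm are 23 × 0.65 = 14.95, taken as 15.

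**Assumptions, because the document gives no figures.** The pre/post correlation r is 0.3, 0.5 or 0.7. Pre-test and post-test SDs are equal (unit SD). Dropout is unrelated to outcome, and tests are two-sided.

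**Formulas**, with N = 23 pre-tests and n = 15 post-tests per arm:

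- Unconstrained mixed model keeping all pre-tests: V1 = 2[(1 − r²)/n + (1 − r)²/N].
- Common baseline mean: V2 = 2(1 − r²)/n.
- With the small-sample cost of estimating the slope: V2* = V2 × [1 + 1/(30 − 4)] = V2 × 1.038.

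At r = 0.5, V1 = 2[0.75/15 + 0.25/23] = 0.1217 and V2 = 2 × 0.75/15 = 0.1000, so V2* = 0.1038. The cut is 1 − 0.1038/0.1217 = 14.7%.

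**Results for an outcome not used for selection, such as quality of life** (detectable effect and power from the noncentral t, 28 versus 27 df; d = 0.8 is assumed):

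| r | V1 | V2 | V2* | Variance cut | SE cut | Effect detectable at 80% power (SD) | Power at d = 0.8 |
|---|---|---|---|---|---|---|---|
| 0.3 | 0.1639 | 0.1213 | 0.1260 | 23.1% | 12.3% | 1.18 → 1.03 | 48% → 58% |
| 0.5 | 0.1217 | 0.1000 | 0.1038 | 14.7% | 7.6% | 1.01 → 0.94 | 60% → 67% |
| 0.7 | 0.0758 | 0.0680 | 0.0706 | 6.9% | 3.5% | 0.80 → 0.77 | 80% → 83% |

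A simulation of 60,000 trials, with the slope estimated in both models, gave variances of 0.1665, 0.1234 and 0.0774 against 0.1260, 0.1043 and 0.0711. Those are cuts of 24.3, 15.5 and 8.1%. Under no effect, every mean estimate was within 0.003 of zero, so neither model is biased.

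**Sensitivity to the comparator.** If only completers entered, as change scores, the planned variance would be 4(1 − r)/n = 0.1867, 0.1333 and 0.0800. The cut after slope cost would then be 32.5, 22.1 and 11.7%. With full retention it would be 33.5, 23.2 and 13.0%. The table is therefore the conservative comparison.

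**BDI-II.** Entry requires a minimum score, which narrows the pre-test spread. If entrants are the top half of a normal distribution (assumed), the pre-test variance falls to k = 1 − 2/π = 0.363 of its unselected value. Taking r as the unselected correlation, V1 becomes 2[(1 − r²)/n + k(1 − r)²/N] = 0.1368, 0.1079 and 0.0708, while V2* is unchanged. The cuts are 7.9, 3.8 and 0.3% by formula and about 9, 4 and 1% by simulation. Power at d = 0.8 moves from 55 to 58%, 65 to 67%, and 83 to 83%.

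**High correlation.** Without selection, the formula gives a cut of 3.2% at r = 0.8 and −0.4% at r = 0.9, where simulation gives about 1%.

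**The case against.** The strongest reply is that the loss is measured against a model the plan never writes down. Section 2.4 does not exclude a common baseline mean or a pre-test covariate, and either would recover the loss. That is true, which is why the claim is tied to the natural reading. But the text speaks of changes and never mentions adjustment, so a programmer following it would most likely fit the unconstrained contrast.

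Second, the size rests on an assumed r, and the upper figure needs r = 0.3. At 0.8 or above there is almost nothing to gain. This stands; the range is conditional and is shown as such.

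Third, depression is the plan's first question, and there the gain is small to nil under selection. This also stands. The larger power gains in the table do not apply to BDI-II unless the pre-test is only loosely tied to the screening score.

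Fourth, some of the document is in the past tense. If outcome data have already been seen, a change to Section 2.4 is no longer pre-specification and would have to be dated and labelled accordingly. The precision argument is unaffected.

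Finally, the conflict over whether BDI-II is an outcome is a separate defect and arguably a more serious one. It is raised here because without a post-test BDI-II no pre/post model can be fitted to that scale.

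**Conclusion.** The concern holds. On its natural reading, Section 2.4 uses a valid, unbiased contrast that is less precise than one available from the same data. With 23 pre-tests and 15 post-tests per arm and equal variances, the avoidable variance for quality of life is about 7% at r = 0.7, 15% at r = 0.5 and 23% at r = 0.3. For BDI-II it is about 0 to 8% over the same range if entrants are the upper half of those screened. The correlation, the degree of selection and the effect size used for power are all assumptions; the document supplies none of them. This is an inefficiency and an ambiguity that should be removed, not an error that invalidates the trial. Fixing a single contrast has value even where the precision gain is negligible.

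**What to change.** In Section 2.4, for each outcome to which the model is applied (depression and quality of life as written):

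- Fit a mixed model to all 46 randomised participants, with time and group-by-time terms, one baseline mean common to both arms, and an unstructured pre/post covariance. Selection on BDI-II makes equal variances at the two times unlikely.
- Alternatively, regress the post-test on group and the pre-test of the same instrument.
- Name one of these as the analysis, and report the adjusted post-test difference with its 95% confidence interval as the effect.

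Reconcile Section 2.1, which lists BDI-II before and after the programme, with the Self-Assessment Questionnaire text in Section 2.3, which limits it to case screening. It must be clear whether the model can be fitted for depression on that scale.

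The cost is one or two sentences in the SAP, a small change to the SAS model statement and the reconciliation above. No participants or assessments are added to those Section 2.1 already lists.

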### 2.5 Aims and objectives

The purpose of this study was to explore the impact of the "Online Mindfulness Cognitive Skills" program on the depressive emotions and quality of life of university students. It was hoped that through the learning of mindfulness cognitive skills, participants would be guided to recognize their irrational thoughts, distinguish automatic thinking, and achieve significant counseling effects. Additionally, participants would be able to apply mindfulness techniques in daily life when experiencing negative emotions, improving self-acceptance, reducing depressive emotions, and enhancing quality of life. The researchers hoped that this study would

provide a deeper understanding of the challenges and living conditions of students with depressive tendencies, and identified which mindfulness techniques are more effective in reducing emotional distress among university students. The goal was to confirm the most suitable mindfulness techniques and behavioral programs for students with depressive tendencies and to explore the advantages of delivering counseling information online to this population. It was anticipated that, following the completion of the study, the promotion of mindfulness cognitive skills through the LINE platform would continue, allowing students at the university to access mindfulness information. The findings were also expected to be valuable for educators, healthcare professionals, and social welfare organizations.

### **3. Informed Consent Form (ICF)**

This study design had been approved by the First Institutional Review Board (IRB) of *Chung Shan Medical University Hospital* (CSMUH No: CS1-22150). Additionally, a *Waiver of Documentation of Informed Consent or Written ICF* was applied for and granted by the *Research Proposal Committee at Chung Shan Medical University Hospital*. Approval details can be found in *Figure 1*. The following points outline the justification for this waiver:

#### **Minimal Risk Design**

The study is designed to pose minimal risk to participants, involving participatory mindfulness exercises and questionnaire surveys without any invasive procedures or treatments. The research activities are expected to cause no discomfort or adverse effects during the execution phase.

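### The plan has no structured adverse-effect question and no pre-specified by-arm count of students who worsened, although pre/post scores would allow such a count among completers

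*Combined protocol and SAP*

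**What the plan says.** All references are to the combined protocol and SAP.

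- **Minimal Risk Design** (section 3, part of the case for waiving documented consent): "The research activities are expected to cause no discomfort or adverse effects during the execution phase".
- **Section 2.1**: "The investigators would evaluate the effectiveness of the two groups using the outcome assessment of BDI-II, WHOQOL-BREF, BAI, OSA, and COPM", at "1 week before intervention (pre-test) and 1 week after intervention (post-test". This covers both arms, with no scored assessment in between.
- **Self-Assessment Questionnaire** (section 2.3): the same instruments are listed "in both pre- and post-tests (with BDI-II used for case screening only". Read literally, that qualification conflicts with section 2.1 and with the depression analysis in section 2.4.
- **Qualitative Feedback Information** (section 2.3): one week after the programme, a questionnaire still to be designed will "evaluate the effectiveness and practicality of the online" mindfulness programme. It mixes rated items with qualitative questions and invites feedback on usage and suggestions.
- **Section 2.4**: "Changes in depression levels and quality of life between the experimental and control groups would be analyzed using a mixed-effects model". The plan also uses "descriptive statistics to record and analyze the basic information and follow-up measurement data of the participants", "described in terms of percentages, means, and standard deviations".
- **Approved Research Design** (section 3): the co-investigator keeps in touch with participants by message each week to look after their well-being. The text does not say what is asked, recorded or reported.
- **Section 2.5**: the investigators anticipate that promotion of the skills through LINE to students at the university will continue after the study.

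**The concern.** Participants are selected for at least mild depressive symptoms, and several programme topics direct attention to mood and to reactions to unpleasant events. Some distress is plausible enough to be worth asking about. The plan states an expectation of none and then specifies no structured way to test it.

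Two kinds of information are at stake. The first is self-reported distress in both arms. If nobody asks the control arm, a between-arm comparison cannot be recovered later. The second is the number of individuals who worsened. A group mean can hold steady or improve while some students deteriorate. A count made after the results are known, with no threshold fixed beforehand, is open to selective choice. Anyone considering wider use of the programme would want that number beside the mean change.

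**Working it through.** **The plan's own figure.** Section 2.2 inflates 30 participants for 35% attrition and states 46. The calculation is 30 / (1 − 0.35) = 30 / 0.65 = 46.15. Strict rounding up gives 47, so the stated 46 agrees apart from rounding (46 × 0.65 = 29.9). Allocation is 23 per arm. If attrition is equal in the two arms, which is an assumption the plan does not state, completers per arm number 23 × 0.65 = 14.95, about 15.

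**What each planned source can show about harm.**

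| Source | Both arms? | What it can show | What is missing |
|---|---|---|---|
| Pre/post scores (2.1) | Yes | Worsening among those with a post-test | No threshold or count planned; nothing between the two time points; nothing on those who leave |
| Mixed model (2.4) | Yes | A worse average change in depression or quality of life | Individual deterioration; BAI is not named for the model |
| Descriptive statistics (2.4) | Yes | Summaries of follow-up scores | No summary of students who worsened is specified |
| End questionnaire (2.3) | Stated subject is the mindfulness programme only | Possibly negative comments in open answers | No harm item described; no control-arm counterpart |
| Weekly messages (section 3) | Not limited to one arm | Concerns noticed by the co-investigator | No recording, classification or reporting stated |

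No row gives a planned harm or deterioration rate by arm. The first row holds the data from which one could be produced for completers. If the BDI-II really were for screening only, there would be no post-test BDI-II, and BAI and WHOQOL-BREF would remain.

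**What harm collection could establish at this size.** With zero events in n students, the exact one-sided 95% upper limit on the true rate is 1 − 0.05^(1/n):

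- n = 23: 1 − 0.05^(1/23) = 12.2%
- n = 15: 1 − 0.05^(1/15) = 18.1%

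The upper end of a two-sided exact 95% interval is 1 − 0.025^(1/n), which gives 14.8% and 21.8%.

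The chance of seeing at least one event in an arm, if events are asked about, is 1 − (1 − p)^n. The documents give no event rate, so p is assumed over a range:

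| Assumed true rate | n = 23 | n = 15 |
|---|---|---|
| 2% | 37% | 26% |
| 5% | 69% | 54% |
| 10% | 91% | 79% |

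**The case against.** A reader might infer that the trial cannot detect or report harm at all, so that any absence of reported harm would only mean nobody asked. The documents do not support that. Three validated symptom or quality-of-life scales are planned before and after in both arms, follow-up scores are summarised, and a worse mean change would appear in the model. Weekly contact gives another route by which trouble could come to light. The end questionnaire has not been written yet, and open questions can draw out bad experiences even when its stated aim is effectiveness and practicality.

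A reader might also infer that the investigators intend to report an absence of adverse effects. The plan never says so. The sentence on adverse effects is an expectation offered in support of a consent waiver. Section 2.5 likewise anticipates further promotion without tying it to any harm rate.

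It is fair to add that a low-risk programme does not need an elaborate safety apparatus, and that parts of the document were removed before review, so absence can be judged only on the text available.

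All of this narrows the point but does not remove it. Scores that could be counted are not the same as a count that is planned. Monitoring without a record yields no rate. A questionnaire about one arm's programme supports no comparison. Low risk justifies light collection, and one item and one table are light.

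**Conclusion.** The point holds in limited form. The available text specifies no structured adverse-effect question, no definition of deterioration and no by-arm summary of individuals who worsened. Deterioration among completers could still be reported from planned scores in both arms. Two things would not be systematically captured: passing distress during the eight weeks, and worsening in students who leave before the post-test, for whom the plan allows 35% attrition.

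The limits of 12.2% and 18.1% should not be read as the size of the defect. They show how little a sample of this size can rule out even with complete collection and no events. The figure of 15 rests on equal attrition across arms, and the detection probabilities rest on assumed rates.

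The change is worth making because it affects what the trial can say about harm, and the self-report part cannot be reconstructed afterwards.

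**What to change.** 1. **Reconcile the role of the BDI-II.** The screening-only wording in the Self-Assessment Questionnaire section must be brought into line with sections 2.1 and 2.4, so that it is clear whether a post-test BDI-II exists.
2. **Add one neutral item, if the questionnaire can still be changed.** One week after the programme, ask both arms whether they had any unpleasant or distressing experience, or felt worse, during the eight weeks, with space to describe it. Report the answers by arm, together with any concerns noted in the weekly messages.
3. **Add one descriptive table to section 2.4.** Show by arm the number and proportion of students whose BDI-II and BAI scores worsened from pre-test to post-test, with exact 95% intervals. Fix the threshold before post-test scores are compared by arm; the available text describes no blinding, so that is the workable cut-off. Show the number without a post-test beside each count, so that losses are visible.

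**Cost.** One questionnaire item and one table, the latter from scores already planned once the BDI-II question is settled. The intervals will be wide. Parts of the text are in the past tense; if data collection has ended, the item is no longer possible, but the table still is, from whatever post-test scores exist.
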